No confinement will be required of subjects in Parts B and D of the study; these subjects will perform all clinic visits in the treatment and follow-up periods as outpatients. During the treatment period of Part B (Day -1 to Day 33), subjects will receive 5 doses of IP, administered 1 dose per week for 5 weeks. During the treatment period of Part D (Day 1 to Day 5), subjects will receive 5 doses of IP, administered 1 dose per day for 5 days. The safety follow-up period will continue up to the last study visit on Day 365 for Part B and Day 341 for Part D.

Figure 1: Study Design Flow Chart

[figure not shown]
Part A

Part B

Part D

See [Table 1](#) through [Table 9](#) for the schedule of procedures and tests to be performed during each of the 3 periods in Parts A, B, and D of the study. Flow diagrams of subject enrollment and treatment allocation are presented in [Appendix 1](#).

In [Part A](#) (SAD groups), 4 groups consisting of 4 subjects each will be enrolled sequentially to receive single doses of MRT5005 or placebo (normal saline) administered by nebulization. Three dose levels of MRT5005 were planned to be investigated: 8, 16, and 24 mg of [REDACTED] mRNA (the active drug substance of MRT5005; nominal dose). An additional treatment group (20 mg) was added after blinded safety information from the 24 mg dose group revealed the occurrence of febrile reactions in 3 of 4 subjects. Within each dose group, the enrollment and treatment of the 4 subjects will be staggered by at least 1 week. Subjects will be randomized in a 3:1 ratio to receive a single dose of either MRT5005 or placebo (3 subjects to receive MRT5005 and 1 subject to receive placebo per dose group). For details on subject enrollment and treatment allocation for Part A, see Section [3.2.1](#).

The PSRC will be responsible for reviewing safety data and, based on this review, making the decision to dose escalate from the 8 mg starting SAD dose level to the 16 mg dose level, and then to the 24 mg maximum dose level. The 20 mg dose level will be evaluated after the 24 mg dose level. The dose escalation process for Part A is described in detail in Sections [3.2.1](#) and [3.4.2](#).

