4.5.6. Study Stopping Criteria

IP administration will be halted for all subjects if any of the following stopping criteria are met:

- a. A subject experiences a Grade 4, life-threatening treatment-emergent AE or death that is considered probably or definitely related to IP by the Investigator
- b. Two or more subjects in a dose group experience 1 or more moderate or severe pulmonary exacerbations during the 5-week treatment period in Part B or through Day 11 (1 week post-5th dose) in Part D
- c. Two or more subjects in a dose group experience an absolute decrease in predicted FEV1 of at least 25 % compared to the baseline value (defined as the average of the Day -1 and Day 1 pre-dose values) during the 5-week treatment period in Part B or through Day 11 (1 week post-5th dose) in Part D that cannot be explained, in the opinion of the Investigator, by the underlying disease of CF and that is confirmed on 2 separate occasions at least 3 days apart
- d. Two or more subjects in the study experience a suspected serious allergic/hypersensitivity reaction, including but not limited to anaphylaxis, generalized rash or bronchospasm likely to be related to drug treatment
- e. Two or more subjects in a dose group experience a deterioration in liver function, as detailed below:
 - i. Elevation of ALT or AST to >5 x ULN in a subject regardless of baseline value
 - ii. Elevation of ALT or AST to >3 x ULN in a subject with a normal baseline or elevation of >3 x ULN from the subject's actual baseline if not normal, with the

appearance of fatigue, nausea, vomiting, right upper quadrant pain or tenderness, fever, rash, and/or eosinophilia (>5%).

- iii. Elevation of ALT or AST to >3x ULN in a subject with a normal baseline or elevation of >3x ULN from the subject's actual baseline if not normal, and total bilirubin >2x ULN or INR >1.5.

To determine whether these stopping rules have been met, all available data relating to the safety of the IP will be reviewed by the PSRC. The treatment assignment of one or more subjects may be unblinded at the request of the PSRC, as described in Section 3.4.1.2. Following this review, the PSRC will decide if the study will:

- Resume unchanged or
- Resume with modifications to the protocol or
- Be terminated.

The Sponsor is responsible for notifying the relevant regulatory authorities and the Investigator is responsible for promptly notifying the relevant IRB of the decision.

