7.2. Part B Study Schedule

Details regarding the procedures and tests to be performed during each study period and time point for Part B are provided in the Schedule of Procedures in [Table 4](#), [Table 5](#), [Table 6](#), and [Table 7](#).

Similar to Part A of this study, Part B will consist of a screening period, a treatment period, and a follow-up period (see [Figure 1](#)). The duration of the screening period is up to 27 days (Day -28 through Day -2); the duration of the treatment period is 36 days (Day -1 to Day 35); and the duration of the follow-up period is up to 332 days (Day 36 through Day 365 [± 3 days]). No confinement (inpatient) will be required of subjects in Part B; subjects will perform all clinic visits as outpatients.

All AEs and SAEs, regardless of relationship, will be collected from the time of informed consent signing until the final study visit on Day 365 (± 3 days). Information on all prior and concomitant medications administered from 30 days before the date of informed consent signing through the final study visit on Day 365 (± 3 days) must be recorded on the appropriate CRF page.

Time Windows for the Schedule of Procedures:

No obligatory time windows are set for the study time points in order to allow for flexibility in the conduct of the study. The time windows provided in [Table 4](#), [Table 5](#), [Table 6](#), and [Table 7](#) are suggested guidelines to be followed during the conduct of Part B. As these guidelines are only suggestions, they will not result in protocol deviations.

Priority Order for Performing Procedures and Tests:

The following priority order will be in effect when more than 1 procedure or test is required at a particular time point.

- AE, concomitant medication, and concomitant surgical procedure reporting
- Vital signs, pulse oximetry
- Physical examination
- Spirometry
- Clinical laboratory tests (serum chemistry, hematology, coagulation, urinalysis, CRP)
- ECG

- Chest x-ray
- Other procedures with lower priorities (weight measurement; blood sampling for [REDACTED] mRNA and [REDACTED] assays, and for immune response assays)

On the days when serum or urine pregnancy testing is being performed, scheduled or unscheduled, this test has priority.

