7.2.1.2. Rescreening of Subjects

Rescreening of subjects, as described in Section [7.1.1.2](#) for Part A, also applies to Part B.

7.2.2. Treatment Period: Day -1 to Day 33

See [Table 4](#) and [Table 7](#) for the Schedule of Procedures for the treatment period of Part B.

Following screening, eligible subjects will return to the study center on Day -1 and will perform the baseline procedures and tests, as described in Table 4. The Day -1 results must be reviewed by the Investigator to ensure that subjects continue to be eligible for study enrollment (see Section [7.1.1.1](#) for definition of screening failure).

Subjects will return to the study center the following day (Day 1). Pre-dose assessments on Day 1 should be performed immediately prior to IP administration; these assessments include a limited physical examination, measurement of vital signs and oxygen saturation (pulse oximetry), and spirometry testing. If the subject is receiving treatment with an inhaled short-acting bronchodilator as part of their routine pulmonary therapies (see below), pre-dose spirometry testing may be scheduled before the subject's pulmonary therapies (if the subject's schedule permits) so that it can be performed "pre-bronchodilator." Alternatively, the subject may choose to delay the bronchodilator treatment until after the pre-dose spirometry testing is performed and receive the treatment just prior to the administration of IP, as described below. Recording of any AEs and concomitant medications should continue at this time. The procedures and tests performed on Day -1 and pre-dose on Day 1 will be used to confirm eligibility; these results will only be exclusionary for subjects if there is a clinically significant or relevant change in a result, as determined by the Investigator (eg, positive pregnancy test).

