At discharge on each dosing day, subjects will be instructed to return to the clinic on the following day (Days 2, 9, 16, 23, and 30). The procedures and tests, as described in Table 4, will be performed at this post-treatment clinic visit. Following these outpatient clinic visits, subjects will be contacted approximately 3 days later by telephone on Days 5, 12, 19, 26, and 33, to query the subject about the occurrence of any AEs/SAEs and any changes in concomitant medications.

If a subject is experiencing respiratory distress or respiratory symptoms, based on the Investigator's judgment, unscheduled spirometry testing may be performed when the subject is stable. In addition, at the discretion of the Investigator, an unscheduled chest x-ray may be performed at any time during the treatment period if the subject is experiencing respiratory symptoms that warrant it.

During the clinic visits and telephone contacts, subjects will be reminded to return to the study center or call the study staff immediately, if they are experiencing any symptoms of concern,

either new or worsening, or were hospitalized or required a visit to the emergency department for any reason.

7.2.3. Follow-up Period: Day 36 to Day 365

See [Table 5](#) and [Table 6](#) for the schedule of procedures for the follow-up period of Part B.

Safety will be monitored for 12 months after administration of the fifth dose of IP in Part B. The safety follow-up period continues through the last study visit on Day 365 (± 3 days).

Subjects will return for outpatient clinic visits on Days 36, 43, 57, 71, 85, 113, 197, 281, and 365 to perform the follow-up procedures and tests scheduled for this period. Telephone contact with the subject will occur on Days 39, 46, 50, 64, 78, 99, 141, 169, 225, 253, 309, and 337 to query the subject about the occurrence of any AEs/SAEs and any changes in concomitant medications. Subjects will also be instructed at every clinic visit and telephone contact to return to the study or call the study staff immediately if they are experiencing any symptoms of concern, either new or worsening, or were hospitalized or required a visit to the emergency department for any reason.

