7.5.2.13. Chest x-ray

Chest x-rays will consist of routine posterioranterior and lateral views.

- For all subjects participating in the study, the baseline chest x-ray may be performed at any time from Day -14 to Day -2 (Parts A and B) or any time from Day -14 to Day -1 (Part D) during the screening period.
- In Part A, chest x-rays are scheduled on Day 8 and Day 29 of the study, representing intervals of 1 and 4 weeks after administration of the single dose of IP.
- In Part B, chest x-rays are scheduled on Day 36 and Day 57 of the study, representing intervals of 1 and 4 weeks after administration of the fifth dose of IP.
- In Part D, chest x-rays are scheduled on Day 11 and Day 32 of the study, representing intervals of 1 and 4 weeks after administration of the 5th dose of IP.

At the Investigator's discretion, a chest x-ray may be performed at any time during the study if the subject is experiencing respiratory symptoms that warrant it.

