## **2.7 Dose Group and Study Stopping Criteria and Unblinding**

Investigational product administration will be halted for all subjects in a dose group, as well as any subjects in an ongoing higher dose group if any of the following stopping criteria are met:

- a. Two subjects in a dose group experience a significant febrile reaction (defined as  $\geq$  Grade 2 fever [ $>39.0^{\circ}\text{C}$ ] associated with systemic symptomatology [eg, body aches, malaise, nausea]) within 24 hours following administration of IP.
- b. Two subjects in a dose group experience a suspected moderate to severe allergic/hypersensitivity reaction, including but not limited to anaphylaxis, generalized rash, edema or bronchospasm possibly related to drug treatment.

Investigational product administration will be halted for all subjects in Part D if the following stopping criterion is met:

- a. Three subjects experience Grade 1 fevers (38.0 to  $39.0^{\circ}\text{C}$ ) associated with systemic symptomatology (eg, body aches, malaise, nausea) onset within 24 hours following administration of IP on  $\geq 3$  separate occasions.

Investigational product administration will be halted for all subjects if any of the following stopping criteria are met:

- a. A subject experiences a Grade 4, life-threatening treatment-emergent AE or death that is considered probably or definitely related to investigational product by the Investigator.
- b. Two or more subjects in a dose group experience 1 or more moderate or severe pulmonary exacerbations during the 5-week treatment period in part B or through Day 11 (1 week post-5th dose) in Part D.
- c. Two or more subjects in a dose group experience a decrease in predicted FEV1 of at least 25 % compared to the baseline value (defined as the average of the Day -1 and Day 1 pre-dose values) during the 5-week treatment period in Part B or through Day 11 (1 week post-5th dose) in Part D that cannot be explained, in the opinion of the PI, by the underlying disease of CF and that is confirmed on 2 separate occasions at least 3 days apart.
- d. Two or more subjects in the study experience a suspected serious allergic/hypersensitivity reaction, including but not limited to anaphylaxis, generalized rash or bronchospasm likely to be related to drug treatment.
- e. Two or more subjects in a dose group experience a deterioration in liver function, as detailed below:

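### The Part B window for the FEV1 and exacerbation stopping rules has no single end day and omits the scheduled Day 36 spirometry, while Part D's window includes its matching Day 11 visit

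*Protocol*

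**What the plan says.** Protocol 4.5.6 opens with "IP administration will be halted for all subjects if any of the following stopping criteria are met". Rule (b) concerns two or more subjects in a dose group with a moderate or severe pulmonary exacerbation. Rule (c) concerns two or more with an unexplained fall in predicted FEV1 of at least 25%, confirmed on two occasions at least 3 days apart. Both apply "during the 5-week treatment period in Part B or through Day 11 (1 week post-5th dose) in Part D". The individual FEV1 rule, 4.5.1(2), has the same window and confirmation clause. SAP 2.7 repeats the study-level rules ("during the 5-week treatment period in part B or through Day 11").

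The Part B treatment period is described in two ways:

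- Protocol 3.1: "During the treatment period of Part B (Day -1 to Day 33". The synopsis, the heading "7.2.2. Treatment Period: Day -1 to Day 33" and SAP 2.3 agree with this.
- Protocol 7.2: "the duration of the treatment period is 36 days (Day -1 to Day 35".

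The next period is headed "7.2.3. Follow-up Period: Day 36 to Day 365", so Day 36 is outside the treatment period on either description. Section 7.5.2.13 has Part B chest x-rays "scheduled on Day 36 and Day 57 of the study, representing intervals of 1 and 4 weeks after administration of the fifth dose" and gives Part D's Days 11 and 32 the same meaning. SAP 9.3, 9.5 and 9.6.1 also use Day 36 for Part B where they use Day 11 for Part D.

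**The concern.** A rule that halts dosing for everyone should have one boundary, and that boundary should take in the visit scheduled to look for harm one week after the last dose. Part D's does. In Part B, a qualifying FEV1 fall first seen at the equivalent visit does not count towards the halt.

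This matters for subjects still being dosed: later subjects in a staggered group, and any other group dosing at the time (Protocol 3.1 lets the 12 mg group run alongside 16 or 20 mg). It matters less for 4.5.1(2), because a subject seen on Day 36 has normally already had all five doses. That rule needs the same wording mainly for consistency.

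**Working it through.** **Inputs.** Part B doses on Days 1, 8, 15, 22 and 29 (Protocol 7.2.2). Part D doses on Days 1 to 5 (7.3.2). Part B spirometry on Days 1, 2, 8, 9, 15, 16, 22, 23, 29, 30, then 36 and 43 (Tables 4, 5 and 7). Part D spirometry on Days 1 to 5, 11 and 18 (Table 8). Dose 5 may be given up to 3 days late, on Day 32 (Table 4, footnote a).

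**The plan's own figure.** With no Day 0, Day -1 to Day 35 is 1 + 35 = 36 days, as Section 7.2 states. Day -1 to Day 33 is 1 + 33 = 34 days. The follow-up of up to 332 days given in 7.2 fits a start on Day 34 (365 - 34 + 1 = 332). From Day 36 it is 330. That slip is clerical.

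**Time covered after dose 5.**

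| Window end | Days after dose 5 |
|---|---|
| Part B, Day 33 | 33 - 29 = 4 |
| Part B, Day 35 (5 × 7) | 35 - 29 = 6 |
| Part B, Day 36 visit | 36 - 29 = 7 |
| Part D, Day 11 | 11 - 5 = 6 |

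On the literal five-week reading, Parts B and D cover the same 6 days. The difference is that Part D's sixth day holds a visit and Part B's does not.

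**Rule (b).** Exacerbations count by when they occur, and each contact asks about events since the previous one (Protocol 7.5.2.3). Onsets through Day 35 reported on Day 36 therefore count. The loss relative to Day 36 is 36 - 35 = 1 day, or 36 - 33 = 3 days on the Day 33 label.

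**Rule (c), confirmation allowed after the window.** Falls first seen on Day 29 or 30 can be confirmed on Day 36. Only a fall first seen on Day 36 is lost.

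**Rule (c), confirmation required inside the window.** First-fall days with a scheduled test at least 3 days later in the window:

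- Part B ending Day 33 or 35: Days 1, 2, 8, 9, 15, 16, 22, 23. Days 29 and 30 fail.
- Part B ending Day 36: Days 29 and 30 are added.
- Part D ending Day 11: Days 1 to 5. A fall first seen on Day 11 waits for Day 18.

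**Doses exposed.** Take the minimum 14-day stagger (starts at 0, 14, 28 and 42) and a fall first seen on Day 36, confirmed on Day 43. If the later affected subject is number 2, calendar day 14 + 43 = 57 leaves 4 same-group doses including that day's, or 2 excluding it. If number 3, day 71 leaves 1 or 0. If number 4, day 85 leaves none. Of the 6 possible pairs, 1, 2 and 3 respectively fall in these cases.

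**Cost in background halts under rule (b).** The documents give no exacerbation rate, so these are assumptions. With p = 1 - exp(-rate × days/365) and independent subjects, the halt chance is P(at least 2 of 4) = 1 - (1-p)^4 - 4p(1-p)^3. At 1 per year over 35 days, p = 0.0914 and the result is 4.43%.

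| Rate per subject-year | 35 days | 36 | 37 | 39 | 64 |
|---|---|---|---|---|---|
| 0.5 | 1.2% | 1.3% | 1.4% | 1.5% | 3.8% |
| 1 | 4.4% | 4.7% | 4.9% | 5.4% | 12.4% |
| 2 | 14.3% | 15.0% | 15.6% | 16.9% | 34.1% |

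Day 64 is 36 + 28: Protocol 7.6 allows a COVID-delayed Day 36 visit within 4 weeks of its target.

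**The case against.** The best defence is that the words five-week already settle the boundary at Day 35, and Day 33 is only the last telephone contact of the period. Part B then has the same elapsed follow-up as Part D. This largely stands. A reader might infer that Part B subjects are watched for materially less time than Part D subjects; on the literal reading they are not.

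Second, the confirmation clause most naturally carries no time limit, since the window attaches to the fall. Unscheduled spirometry is also allowed for respiratory symptoms (Table 4, footnote n; Protocol 7.2.2 and 7.2.3). So it would be too strong to say that falls after dose 5 cannot be confirmed. That holds only for scheduled tests on the stricter reading, but the text does not rule that reading out.

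Third, a dose 5 given on Day 32 might seem to leave only 1 day of window under the Day 33 label. Table 4, footnote a ties Week 5 contacts to actual dosing, so the contact that marks Day 33 would move to about Day 36, still about 4 days after the dose.

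Fourth, a Day 36 visit may be held on Day 35 within its suggested one-day window, and the PSRC can act on any safety data. Both are true. Neither makes a fall seen on Day 36 count towards the rule.

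**Conclusion.** The point holds as a minor but real defect. There are two stated end days for one stopping window. The scheduled one-week spirometry is outside that window in Part B and inside it in Part D. The FEV1 rules are silent on whether confirmation may follow the window.

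The exacerbation rule loses about one day on the literal reading. The FEV1 rule loses a fall first seen on Day 36 and, on the stricter reading only, scheduled confirmation of falls first seen on Day 29 or 30. At the minimum stagger, 0 to 4 same-group doses remain when a Day 36 fall is confirmed on Day 43, with none left for 3 of the 6 subject pairs.

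A reader might infer that safety signals after dose 5 go unreviewed. The documents do not support that: the PSRC sees the data and may act, and study rules (a), (d) and (e) carry no such window. What the change gains is the predefined halt.

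**What to change.** - In Protocol 4.5.6(b), 4.5.6(c), 4.5.1(2) and SAP 2.7, replace the Part B wording with: through Day 36 (1 week post-5th dose, including its +1 day visit window), or 7 days after the actual fifth dose if later. With dose 5 no later than Day 32, this ends by Day 32 + 7 = Day 39. It should be a study-day limit, not tied to when the visit takes place, because a COVID-delayed visit could otherwise stretch the window to Day 64.
- In the FEV1 rules, for both Parts, state that the first fall must occur in the window and the confirming test may follow it. Falls first seen on Day 29, 30 or 36 in Part B and on Day 11 in Part D can then all count.
- Use one Part B treatment-period label, Day -1 to Day 35, in the synopsis, Protocol 3.1 and 7.2.2, and SAP 2.3. Correct 332 to 330 follow-up days in 7.2 at the same time.

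The cost is wording only: no added visit, test or subject. The downside is a slightly higher chance of a halt from background exacerbations. At an assumed 1 per subject-year it goes from 4.4% over 35 days to 4.7% over 36, 4.9% if the one-day allowance is used, and 5.4% at the Day 39 limit. Such a halt leads to PSRC review, which may let dosing resume unchanged.

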5. PRIOR AND CONCOMITANT TREATMENT AND PROCEDURES

5.1. Prior and Concomitant Medications and Therapies

Information on all prior and concomitant medications administered from 30 days before the date of informed consent signing through the final study visit on Day 337 (± 3 days) in Part A, Day 365 (± 3 days) in Part B, or Day 341 (± 3 days) in Part D of the study must be recorded on the appropriate CRF page. This includes the subject's routine and non-routine CF medications, other medications, and herbal and homeopathic preparations.

All therapies being taken by the patients on entry to the study or at any time during the study are regarded as concomitant therapies and will be documented on the appropriate pages of the CRF. These include but are not limited to airway clearance techniques.

5.1.1. Permitted Medications and Therapies

Subjects should remain on a stable medication regimen for CF from at least 28 days prior to the screening visit through the final study visit on Day 337 (± 3 days) in Part A, Day 365 (± 3 days) in Parts B, or Day 341 (± 3 days) in Part D of the study. These may include but are not limited to routine inhaled therapies directed at airway clearance and management of respiratory infections, such as bronchodilators, rhDNase (PULMOZYME), hypertonic saline, antibiotics, and steroids; and other routine CF-related therapies such as systemic antibiotics, pancreatic enzymes, multivitamins, and diabetes and liver medications. The timing of subject participation and routine treatment with cycled inhaled antibiotics will be left up to the discretion of the Investigator.

Hormone replacement therapies, thyroid hormone replacement therapy, and non-steroidal inflammatory drugs are also permitted.

Any other medications which are considered necessary for the subject's safety and well-being may be given at the discretion of the Investigator. For example, for subjects experiencing a pulmonary exacerbation, therapeutic interventions may include oral or intravenous administration of antibiotics, oral or parenteral nutritional support, frequent airway clearance techniques, augmented bronchodilator therapy, and corticosteroids.

Other specific medications permitted during the study are listed below:

- Hormonal contraceptives for females of childbearing potential administered according to the package insert (see Section 4.4.1).
- Lumacaftor/ivacaftor combination drug (ORKAMBI) or tezacaftor/ivacaftor combination drug (SYMDEKO). For Part D only: elexacaftor/tezacaftor/ivacaftor triple combination (TRIKAFTA). To be eligible, subjects must have been on stable treatment with these medications for at least 28 days prior to the screening visit and should remain on it for the duration of the study.

Subjects should remain on their routine CF therapies, which include but are not limited to airway clearance techniques.

